Statistical Methodology	
Chi Square and descriptive statistics used for questionnaire responses.
 
Mann Whitney U test for dosing adjustments and time until first anticoagulation.
 
Students t test or Mann Whitney U for dosing changes required, time until therapeutic anticoagulation, and percentage of time therapeutic anticoagulated

	Concordance assessed with mixed effects model; repeated measures ANOVA and Turkey's test for multiple comparisons to analyze heparin administration. Clinical outcomes will be compared with a Chi square test. Intention to treat analysis will be used.
--	---

A Background and Rationale

Mechanical Circulatory Support

The prevalence of heart failure in the United States currently exceeds five million and continues to rise.¹ It remains the primary diagnosis in over one million hospitalizations annually, with an economic burden exceeding \$30 billion in the United States.² People with severe heart failure and symptoms at rest may be treated with mechanical circulatory support (MCS) pumps, such as a left ventricular assist device (LVAD). This pump is used as a long-term destination therapy or as a bridge to receiving a heart transplant. As the number of organ donors remains relatively fixed, and conventional medical therapies fail, MCS is increasingly utilized in this patient population with total implants approaching 2,500 per year.³

Complications of Mechanical Circulatory Support

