Anti-Xa 0.3-0.7 IU/mL	None	No change
Anti-Xa 0.71-0.80 IU/mL	None	Decrease 1 unit/kg/hour
Anti-Xa 0.81-0.99 IU/mL	Hold infusion for 30 minutes	Decrease 2 units/kg/hour
Anti-Xa greater than 0.99 IU/mL	Hold infusion for 1 hour	Decrease 3 units/kg/hour

Draw STAT anti-Xa 6 hours each rate change.
Once two consecutive anti-Xa's are therapeutic (0.3-0.7 IU/mL), then draw anti-Xa every am.
Draw CBC Express every 72 hours until heparin is discontinued.

Duration of Study:

Patients will be followed for 14 days of heparin therapy or until heparin has been discontinued (e.g. changed to bivalirudin for anticoagulation or completed a transition to warfarin) if sooner than 14 days. If the patient has not received any IV heparin for 5 consecutive days they will be considered to have failed anticoagulation and the reason noted by the clinical team for discontinuation will be recorded.

The requirement for clinical team training and feedback:

A necessary first step in embarking on this feasibility trial is to train the clinical staff in the use of algorithms for IV UFH administration postoperatively in patients following implantation of the LVAD. It is important first to show that nomograms are practical such that clinicians can easily follow them, and second that by following the nomograms the target parameters are achieved. The collaborators in this study represent the key stakeholders responsible for the management of patients with LVADs in the postoperative period. As such, there is commitment from medical, nursing and pharmacy leadership to manage heparin administration based on either the current aPTT based or the new anti-Xa based nomogram (Table 2). During the feasibility phase, all the medical and nursing staff will undergo structured training in the rationale behind and implementation of the nomograms. Structured training will take place through formal physician and nursing in-services provided by our clinical nurse specialist and clinical pharmacist specialist. The training will include background information, practical advice, mock scenarios, trouble shooting and safety tips. To assess impact, questionnaires for the nurses taking care of the study patients will be handed out by the research team on each nursing shift. The research team will collect the completed forms for input into the database.

Risks and mitigation efforts:

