The potential serious risks attributable to avoiding anticoagulation as well as providing heparin and warfarin anticoagulation are well known and include gastrointestinal bleeding, mediastinal bleeding, retroperitoneal bleeding, stroke, LVAD thrombosis, and potentially death. As these are known and anticipated, they will be reported annually to the IRB. All unexpected adverse events associated with research participation or study intervention will be reported to the WUSTL IRB per their Reportable Event Reporting guidelines [WUSTL IRB Policies and Procedures, Section X]. All safety events, including adverse events and/or laboratory abnormalities identified in the protocol as critical to safety evaluations will be reported to the PI in a timely fashion.

The specific monitoring plan for this investigation is commensurate with the risks and the size and complexity of the investigations planned with this feasibility trial. Should there be an unanticipated serious adverse event that potentially increases the risks to the participants, the study will be stopped, an investigation will be conducted by the PI and research team members, and a findings report will be generated and submitted to IRB before the study is resumed. The safety data will be monitored and reviewed every 3 months.

E Statistical Plan

Sample size:

For the planned feasibility study, we have selected a convenience sample of 20 patients; 10 patients randomized to the anti-Xa monitoring arm and 10 patients randomized to the aPTT monitoring arm. Data collected on subjects that were excluded based on receipt of an additional pumping device during the index surgery but prior to randomization will not be included in the dataset. Data from subjects excluded based on receipt of an additional pumping device after randomization will be retained and analyzed up to the point of withdrawal from the study.

No power analysis is planned for this feasibility trial.

Descriptive statistics will be performed looking at the study groups.

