For feasibility, questionnaires completed by the nursing staff evaluating the practicality and acceptability of the nomograms will be analyzed with descriptive statistics and compared between the two groups using a Chi square test. The percentage of correct dosing adjustments made by the nursing team required to achieve first therapeutic anticoagulation will be compared between the two groups using a Mann Whitney U test. For success, the number of dosing changes required to achieve first therapeutic

anticoagulation, the time (in hours) to achievement of first therapeutic anticoagulation, and the percentage time therapeutic anticoagulation remains after it is achieved will be compared between the two groups using a Student's t-test if data is normally distributed or a Mann-Whitney U test if data is not normally distributed.

If possible based on population size, concordance between groups of aPTT and anti-factor Xa activity will be assessed with a suitable (parametric or non-parametric) mixed effects statistical model. This approach is likely to yield more accurate information than crude correlation assessments that have been used in other studies, which have not taken into account repeated measures within patients. We will use repeated measures ANOVA and Tukey's test for multiple comparisons to analyze heparin administration in the two groups. With a mixed effects model, we will compare heparin dose in the two groups, while controlling for confounders, including the effect of time on the dose of heparin administered, and assuming an autoregressive covariance structure (the nature of the correlations between measurements for the same patient), as well as a random intercept to allow for some of the effect of potential unknown confounders.

If possible based on study size, markers of gastrointestinal bleeding, major bleeding, neurologic events, and thrombotic complications will be compared with a Chi-square test. Additionally, as able, adjusted logistic regression will be used to explore risk factors for complications. We will use intent-to-treat approach in our analyses. We will also use appropriate imputation methods and test the sensitivity of our results. No imputation is planned for missing primary outcomes data.

F Data Handling and Record Keeping

Data Collection and Methods

All questionnaire's performed will be collected and responses recorded.

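### Heparin dose by arm has two planned analyses and no stated lead; the mixed model already planned should be the only one

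*Combined protocol and SAP*

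**What the plan says.** Section B (Study Objectives) lists heparin dosing among the secondary outcomes, to be explored. Section E gives two analyses of it in consecutive sentences. The first is "We will use repeated measures ANOVA and Tukey's test for multiple comparisons to analyze heparin administration in the two groups". The second is "With a mixed effects model, we will compare heparin dose in the two groups", adjusting for confounders that include time, "assuming an autoregressive covariance structure" and with a random intercept per patient. Neither is called the main analysis.

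The Statistical Methodology row of the synopsis differs. It reads "Concordance assessed with mixed effects model; repeated measures ANOVA and Turkey's test for multiple comparisons to analyze heparin administration", so the mixed model is attached to concordance only, and heparin dose has the ANOVA and Tukey's test alone.

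On the length of the series, section C (Duration of Study) says "Patients will be followed for 14 days of heparin therapy or until heparin has been discontinued", if that comes before 14 days. Under Sample size in section E, data from patients withdrawn because they received an additional pumping device after randomization "will be retained and analyzed up to the point of withdrawal from the study". There are two arms: "10 patients randomized to the anti-Xa monitoring arm and 10 patients randomized to the aPTT monitoring arm". Section E also promises unspecified imputation and sensitivity checks, and rules out imputation only for primary outcomes.

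**The concern.** A classical repeated-measures ANOVA needs every patient measured at every time point. This design does not produce such a grid, because each patient's series ends when heparin ends or the patient is withdrawn. The analyst has three ways out, and each has a cost:

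- Dropping patients who stop early selects on something that happens after randomization, so the arms compared are no longer the arms randomized.
- Cutting to a window that all patients share keeps every patient but loses days.
- Imputing doses after heparin has stopped changes the question, because those doses are not missing values: heparin was not being given.

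The mixed model avoids all three, but the plan does not make it the lead. Two results for one outcome could disagree, with no rule for choosing between them. A reader of the synopsis would take the weaker method as the plan. The role of Tukey's test with two arms is not explained.

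**Working it through.** **1. Figure in the plan.** The only one is the sample size, 10 + 10 = 20, which agrees. No alpha, effect size, SD or power is stated, and no heparin duration is given.

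**2. Data lost if only complete 14-day series are used.** Let *s* be the share of patients still on heparin at day 14. It is an assumption, varied over a wide range. With a constant daily stopping rate *h*, (1 − *h*)^13 = *s*, so *h* = 1 − *s*^(1/13).

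- Observed patient-days = 20 × Σ (1 − *h*)^(d−1), d = 1 to 14
- Patient-days used = 20 × *s* × 14
- Share discarded = 1 − used / observed

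| *s* | Patients kept of 20 | Observed patient-days | Used | Discarded |
|---|---|---|---|---|
| 0.90 | 18 | 265.8 | 252 | 5% |
| 0.75 | 15 | 243.5 | 210 | 14% |
| 0.50 | 10 | 202.6 | 140 | 31% |
| 0.25 | 5 | 153.3 | 70 | 54% |
| 0.10 | 2 | 112.9 | 28 | 75% |

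For *s* = 0.25, P(an arm of 10 has at least 2 completers) = 1 − 0.75^10 − 10 × 0.25 × 0.75^9 = 0.756. The chance that at least one arm has fewer than 2 is therefore 1 − 0.756² = 43%.

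A full 14-day grid is unlikely even in the mildest case: for *s* = 0.90, all 20 patients complete with probability 0.90^20 = 12%.

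**3. What dropping patients could do to the estimate.** This was simulated with no true arm difference and 150 trials per setting. All settings are assumptions: between-patient SD 2.5 and within-patient SD 1.5 units/kg/hour, lag-1 correlation 0.6, and a daily stopping probability of 3% or 10%. Stopping was either unrelated to dose or, in one arm only, more likely at lower dose. The mixed model had a random intercept and day effects but no autoregressive term.

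| Stopping | Daily rate | Completers only: mean (SD) | Mixed model: mean (SD) |
|---|---|---|---|
| Unrelated to dose | 3% | +0.24 (1.53) | +0.10 (1.16) |
| Unrelated to dose | 10% | +0.05 (2.50) | +0.05 (1.17) |
| Dose-related in one arm | 3% | +0.94 (1.36) | −0.01 (1.07) |
| Dose-related in one arm | 10% | +1.98 (1.99) | −0.08 (1.27) |

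At the 10% rate, 16% of trials had an arm with no completer and gave no completers-only estimate. The Monte Carlo error of the first completers-only mean is 1.53/√150 = 0.12, so its +0.24 is within about two standard errors of zero. The false differences of 0.9 to 2.0 units/kg/hour can be set against the 1 to 3 units/kg/hour steps of the nomograms.

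**4. Tukey's test with two arms.** There is one pair. The studentized range critical value divided by √2 is 2.101 on 20 − 2 = 18 df, and the two-sided 5% t value is also 2.101. The two tests are the same. Applied to 14 days instead, Tukey's test makes 14 × 13 / 2 = 91 pairs. Applied to 28 arm-by-day means it makes 28 × 27 / 2 = 378, of which 14 compare the arms on the same day. The plan does not say which is meant.

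**The case against.** The strongest reply is that the plan already contains the right analysis. The mixed model includes time and serial correlation, accepts unequal follow-up and gives an arm contrast. That stands, and it is the main reason the point is minor. It leaves open which analysis leads, and it does not repair the synopsis.

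A second reply is that imputation is promised and is not excluded for secondary outcomes, so dropping patients or days is not forced. This is also true. But an imputed dose after discontinuation would need its own definition, and none is given.

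A reader might infer more than the documents support:

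- *That the ANOVA answers no two-arm question.* With arm as the between-patient factor it tests arm and arm-by-time. Only the Tukey step is redundant.
- *That the arm comparison will be biased.* Selection arises only if patients are dropped. A common early window keeps everyone randomized, and the planned mixed model does not need complete series.
- *That most of the data will be lost.* This holds only if few patients are still on heparin at day 14. At 50% the loss is 31%. The 14-day daily grid is itself an assumption, since the plan names no time unit.
- *That Tukey's test will spread error over 378 comparisons and nearly double the interval width (critical value 3.76 against 1.97).* Those values use 18 × 13 = 234 df, which needs all 20 patients complete for 14 days. They cannot be combined with a claim that few reach day 14, and the plan never says that Tukey's test is applied to arm-by-day means.

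**Conclusion.** The point holds as a minor one. Two analyses are named for heparin dose by arm with no order between them, and the synopsis lists only the one that fits the design less well. Unequal series are built into the follow-up rule, so a classical repeated-measures ANOVA cannot be run without dropping patients, losing days or defining doses after heparin has stopped. On the complete-series route, the loss runs from about 5% to about 75% of observed patient-days as the assumed share still on heparin at day 14 falls from 90% to 10%. The documents do not say where in that range the trial will lie. The simulated bias shows what is possible under assumed dose-related stopping in one arm; it does not predict what will happen here. Tukey's test adds nothing to a two-arm contrast whatever is assumed. No primary feasibility or success measure uses the ANOVA, and the sample is a convenience sample of 20 with no power claim.

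**What to change.** Delete the repeated-measures ANOVA and Tukey's test for heparin dose from section E and from the Statistical Methodology row of the synopsis. State in both places that the mixed model already planned is the single arm comparison of heparin dose and uses all observed on-heparin data from every randomized patient. Name one contrast: the mean difference between arms in units/kg/hour over the nomogram period. Include device type, the stratification factor, as a covariate, and state the time unit (day, draw or rate change) on which the autoregressive correlation is defined.

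The cost is a few lines of wording and one analysis fewer, with no added data collection. With 20 patients the model may not converge with both an autoregressive term and a random intercept, so a simpler covariance should be named in advance as the fallback.
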